8.3. Variables

There are two primary baseline periods of interest from which variables of interests will be evaluated: 1) 12-months fixed pre-index period and 2) a variable length baseline period is the maximal continuous enrollment window prior to index and at least 1-year pre-index. The primary post-index period is 12 months including the index date. Other observation periods are noted below.

Variable	Role	Data source(s)	Operational definition
Demographics (Table 1)		
Age	Baseline Characteristic	All	Age will be defined as of the index year.
Age groups	Baseline Characteristic	A11	Patients will be assigned to one of the following age groups based index age: 18–44, 45–64, and 65yo.
Gender	Baseline Characteristic	All	Gender will be captured from enrollment data.
Insurance type	Baseline Characteristic	All	Whether the patient was covered under a commercial or Medicare Supplemental (Truven DataType) insurance plan will be captured.
Plan type	Baseline Characteristic	All	HMO, EPO, GPO, etc via.
			PlanType.
Geographic region	Baseline Characteristic	All	The United States (U.S.) region in which the study patient is enrolled in a health plan will be determined and reported and states will be categorized into five geographic regions: Northeast, South, Midwest, West, Unknown (https://www2.census.gov/geo/pdfs/maps- data/maps/reference/us_regdiv.pdf).
Variable length baselin	eBaseline Characteristic	All	Identify the duration of variable length (ie, all available pre-index continuous enrollment) baseline period.

Variable	Role	Data source(s)	Operational definition
RA-Related Medication	Use in Pre-Index (Tabl	e 2)	
Pre-index biologic DMARD use	Baseline Characteristic	All	A count of unique (on different days) pharmacy/admin claims on different days for ADA/ETN will be created during the 12 month baseline period.
Time from last pre- index bDMARD to index	Baseline Characteristic	All	A variable for the interval between last ADA/ETN pharmacy/administration claim and index. Stratify by <3 mos, 3-<6 mos and 6-12 mos pre-index.
Time from first pre- index bDMARD to index	Baseline Characteristic		A variable for the interval between first ADA/ETN pharmacy/administration claim during the variable length baseline and index. Stratify by <6, 6-12, ≥12 mos.

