Comorbidities of interest	Baseline Characteristic	All	 0/1 flags will be created to identify the presence of the following comorbidities during the 12-month baseline period (see Appendix 4). Cardiovascular diseases. Chronic obstructive pulmonary disease (COPD). Asthma. Kidney disease. Diabetes. Depression. Anxiety. Liver disease. Sleep disorders. Hypertension. Hyperlipidemia. Interstitial lung disease.

Variable	Role	Data source(s)	Operational definition
Cumulative OOP Costs pre-index	Baseline Characteristic	All	The total, pharmacy and medical OOP costs (deductible+copay+coinsurance) resource use from January 1 of index year through Index.
Index Date OOP costs	Baseline Characteristic	All	Total, pharmacy (excluding index medication) and medical OOP costs on index date.
Index Medication (Table	4)		
Index Prescriber	Baseline Characteristic	All	Top 5 index medication prescriber specialties and other or unknown will be identified.
Index month/year	Baseline Characteristic	All	The month and year of the patient's index date (start of TOFA, ETN, ADA) will be identified.
Index Medication OOP costs	Baseline Characteristic	All	The index medication pharmacy OOP costs (deductible+copay+coinsurance) will be identified for the first index medication rx and cumulative by month (1-12) of follow-up (only looking at pharmacy claims here noting index event is a prescription fill).
Index combination vs. monotherapy regimen status	Baseline Characteristic	All	Patients with a use of one of the 4 main NB- DMARDs (injectable and oral MTX, SSZ, HCQ, LEF) within 90 days on or after the index date will be considered as being treated with combination therapy regimen, others will be classified as monotherapy. For monotherapy, will evaluate 6-mos pre-index use of each of the four main and other NB- DMARDs. For combination regiment, will stratify by 6 mos pre-index use of the four main and other NB-DMARDs.
Post-Index Treatment Pa	tterns (Table 4)		
Treatment Persistence (5 groups)	Outcome	All	Persistent with the index medication will be defined as not having a gap in therapy of at least 60 days between fills/admins. For retail pharmacy (rx) claims the day supply will be utilized and rounded to the nearest 28-day supply for ETN and ADA and 30- day supply for TOFA. For subcutaneous ETN and ADA administrations, a 28-day supply will be assumed.

Variable	Role	Data source(s)	Operational definition

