			4.No adding of a new non-biologic DMARD to the index therapy.
			Measure has been modified to
			distinguish outcomes for advanced
			monotherapy vs. NB-DMARD
			comobination regiments, noting
			patients may not have NB-DMARD in
			6-mos pre-indes but start a
			combination regimen. For those
			starting a monotherapy index
			medication regimen, the initiation of a
			select NB-DMARD will be identified
			in the follow up period as addition of
			NB-DMARD. For those starting a
			combination index medication
			regimen, presence of a different NB-
			DMARD in follow-up will be flagged
			as failing the algorithm.

Variable	Role	Data source(s)	Operational definition
			5. Oral glucocorticoids. Only National Drug Code (NDC) codes for oral glucocorticoids will be included.
			5a. For patients with no claims for oral glucocorticoid prescriptions in the six months prior to the index date: cannot receive more than 30 days of oral glucocorticoids between (index date + 89) to (index date + 359). 30 days of oral glucocorticoids will be determined by summing up the day supply of all glucocorticoids claims with a fill date between (index date + 89) to (index date + 359).
			5b. For patients with claims for oral glucocorticoids during the six months prior to the index date: No increase in oral glucocorticoid dose ≥20% during months 6- 12 after index compared to the 6 months before the index date. Increase in oral glucocorticoids will be determined from the prednisone equivalent dose for all glucocorticoid claims filled during the respective time periods.
			6. At most one parenteral or intra- articular glucocorticoid joint injection on unique days after the patient had been on biologic treatment for more than three months between (index date + 89) to (index date + 359). CPT codes 20600, 20605, 20610.
Change in Resource Use RA-related healthcare	and Costs (Tables 5 an Outcome	all	The number of patients with and number of encounters
resource use		- 141	(including zeros) for each RA- related medical and pharmacy resource use will be evaluated in the 12-month pre- and post-index periods. See Section 8.3.1 for details on calculating cost and healthcare utilization.
All-cause healthcare resource use	Outcome	All	The number of patients with and number of claims (including zeros) for each all-cause medical and pharmacy resource use will be evaluated in the 12-month pre- and post-index periods. See Section 8.3.1 for details on calculating cost and healthcare utilization.

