8.7.4. Multivariate Analysis

To control for possible confounding of the relationship between the outcomes and independent variable of interest, select objectives will be conducted utilizing multivariable methods as described above.

Final outcomes for multivariate analysis will be selected after review of descriptive results. Possible outcomes of interest include: total all-cause health care cost, total RA-related health care cost, cost of bDMARDs/tofacitinib/administration/NB-DMARDS, medication effectiveness (yes vs. no).

For each model, specific predictors to be included will be determined based upon clinical rationale and statistical significance. Variables listed in Section 8.3 will be considered for inclusion in the multivariable models. Additional variables identified throughout the course of the study will also be considered. Following standard procedure, regression diagnostics will be performed for each model to assess goodness of fit and violations of model assumptions (eg, multicollinearity, heteroskedasticity). When there are violations of the model, programmers will note them and make appropriate corrections to the data (ie, typically through transformation of either the independent or dependent variables) or in the method of estimation.

In particular, generalized linear models will be fit, using appropriate distributions and links for the nature of the data (eg, normally-distributed data with identity link, binary data and logit link). Results will be displayed on the original scale (that is, the inverse link). If sufficient sample size, tofacitinib IR and tofacitinib XR will be treated as separate groups. That is, contrast statements will be used to average the two groups when comparing to bDMARDs. Point estimates (that is, mean differences, ratios, odds ratios), 95 percent confidence intervals, and p- values will be presented for contrasts; ANOVA table will be presented to display the strength of the independent variables, including point estimates and p-values.

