8.7.5. Cost Data

Because health care costs are often skewed, estimated cost measures will be modeled using a gamma regression model. Coefficients from a generalized linear model (GLM) are estimated cost ratios. Cost ratios, 95 percent confidence intervals, and p-values will be presented for each covariate included in the final model. For ease of interpretation and comparison with the bivariate results, the average cost will be predicted for each cohort and may also be predicted for pre-determined levels of other patient characteristics (eg, combination vs. monotherapy, gender).

If a significant number of patients have zero values for costs, estimated cost measures will be compared using a two-part model (ie, one equation estimating the probability of any cost and a GLM with a gamma distribution and log link estimating the level of cost). This method avoids potential difficulties introduced by transformation and retransformation of the dependent variable.

If there is an excessive number of zero-dollar cost patients, then only logistic regression prediciting the probability of nonzero costs will be run.

Odds ratios, 95 percent confidence intervals, and p-values will be presented for each covariate included in the logistic model estimating the probability of non-zero costs. Cost ratios, 95 percent confidence intervals, and p-values will be presented for each covariate included in the GLM model estimating the level on costs. Combined results will displayed.

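### Combination/monotherapy status is labelled baseline but is set by fills up to 90 days after index, so it is unsafe as a covariate and hides some first NB-DMARD additions

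*Combined protocol and SAP*

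**What the plan says.** The variable table in Section 8.3 carries the row "Index combination vs. monotherapy regimen status Baseline Characteristic". Patients using methotrexate, sulfasalazine, hydroxychloroquine or leflunomide "within 90 days on or after the index date will be considered as being treated with combination therapy regimen"; "others will be classified as monotherapy". Use in the 6 months before index does not set the class. For combination patients the plan "will stratify by 6 mos pre-index use of the four main and other NB-DMARDs", and for monotherapy patients it describes the same history. The opening of Section 8.3 states that "The primary post-index period is 12 months including the index date", so the whole 90-day window is follow-up.

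The label is then used in three places:

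- **Models.** Section 8.7.4: "Variables listed in Section 8.3 will be considered for inclusion in the multivariable models".
- **Predicted costs.** Section 8.7.5 allows predictions at pre-determined levels of patient characteristics ("eg, combination vs. monotherapy, gender").
- **Outcomes.** In criterion 4 of the effectiveness proxy (Section 8.3), for patients starting on a monotherapy "medication regimen, the initiation of a" select NB-DMARD counts as an addition. Combination starters fail only on a different NB-DMARD. The NB-DMARD use row of the same table likewise evaluates addition only in patients classed as starting monotherapy, and it identifies the select agents as the four main ones.

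**The concern.** A covariate treated as baseline should be fixed when follow-up starts. This one can be set by what happens during the next 90 days, and the rule does not ask whether the patient is still on the index drug. Someone who stops it on day 30 and first fills methotrexate on day 60 is classed as combination. If such starts are related to how the index drug is doing, the flag carries outcome information into any model that uses it, and regimen-level predicted costs inherit the distortion.

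The same rule feeds an outcome. Among patients with no main NB-DMARD at index, a first one added in the first 90 days changes the class rather than counting as an addition. The effectiveness proxy is a named secondary outcome (Section 7.2), and failing any one of its six criteria makes a patient not effectively treated.

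**Working it through.** The plan states no add-on rate, sample size or power relevant here, so there is no planned figure to reproduce. All rates below are assumptions.

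**1. Criterion 4 applied as written**

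- No NB-DMARD at index, first methotrexate on day 60: combination; passes.
- Same patient, first methotrexate on day 100: monotherapy; fails.
- Methotrexate on day 0, hydroxychloroquine added on day 40: combination; fails if different means different from the agent used at index, passes if the regimen is every main agent filled in the window. The text does not say which.
- Methotrexate on day 0, hydroxychloroquine added on day 120: fails on either reading.

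**2. Share of first add-ons hidden**

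Let p be the annual probability that a true monotherapy starter first adds a main NB-DMARD, with constant hazard over 360 days. The share falling in the window is [1 − (1 − p)^(90/360)] / p:

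- p = 5%: 0.0127/0.05 = 25.5%
- p = 10%: 0.0260/0.10 = 26.0%
- p = 20%: 0.0543/0.20 = 27.1%
- p = 30%: 0.0853/0.30 = 28.4%
- p = 40%: 0.1199/0.40 = 30.0%

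A true 20% shows as 20 − 5.4 = 14.6%, and a true 10% as 10 − 2.6 = 7.4%, so a 10.0-point cohort contrast in additions shows as 7.2 points. Add-on concentrated early would hide more.

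**3. Spurious regimen coefficient**

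Assume half of patients use an NB-DMARD at index, it has no effect on persistence, stopping is exponential with 45% persistent at day 360, and a fraction q of non-users who stop before day 60 (and no continuers) start an NB-DMARD by day 90.

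- λ = −ln(0.45)/360 = 0.002218 per day.
- Mean duration to day 360 = 0.55/0.002218 = 248.0 days.
- P(stop before day 60) = 1 − 0.45^(1/6) = 0.1246.
- Mean duration of those early stoppers = 1/λ − 60 × 0.8754/0.1246 = 29.3 days.
- Combination mean = (248.0 + 0.1246q × 29.3)/(1 + 0.1246q); monotherapy mean = (248.0 − 0.1246q × 29.3)/(1 − 0.1246q).
- q = 10%: 245.3 − 250.7 = −5.4 days. q = 20%: −10.9. q = 30%: −16.4.

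A simulation of 1,000,000 patients gave −5.8, −11.3 and −16.9 (−0.5, noise, with a pre-index definition). The result depends on who starts. With equal add-on in stoppers and continuers it is 0. With 10% in early stoppers and 20% in continuers it reverses to about +5.6 days: continuers average (248.0 − 0.1246 × 29.3)/0.8754 = 279.1 days, giving 250.3 − 244.6.

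**4. Effect on the cohort contrast**

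In a linear model, the shift in the cohort contrast from adjusting for the flag is minus the flag coefficient times the cohort difference in flag prevalence. Take 45% versus 55% persistence (early-stop probabilities 0.1246 and 1 − 0.55^(1/6) = 0.0948). The flag coefficients below are least-squares values.

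- NB-DMARD use 50% in both, q = 30%: prevalence 0.5187 and 0.5142; coefficient −15.1; shift 15.1 × (0.5142 − 0.5187), under 0.1 day in size. With 35% versus 55% persistence it is still at most 0.2 day.
- Use 30% versus 70%, q = 10%: prevalence 0.3087 and 0.7028; coefficient −6.14; shift 6.14 × 0.394 = 2.4 days.
- Use 30% versus 70%, q = 30%: prevalence 0.3262 and 0.7085; coefficient −18.3; shift 18.3 × 0.382 = 7.0 days.

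**The case against.** The plan has a reason for the label: Section 8.3 notes that patients may have no NB-DMARD in the 6 months before index and still start a combination. Stratifying combination patients by pre-index use exposes new starters. Pre-index NB-DMARD use is itself a candidate covariate. Using the regimen flag as a covariate, or for predicted costs, is permitted rather than fixed. All of this stands. It does not remove the point: the stratification does not carry into criterion 4, cannot separate a day-0 start from a day-60 add-on, and does not make the label baseline.

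Three stronger inferences are tempting and not supported:

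- *The flag biases the primary cohort comparison.* Persistence is defined without it, and adjusting for it barely moves the contrast when NB-DMARD use is similar across cohorts. The documents give no figures on that balance.
- *Early add-on can never count as failure.* A patient already on one NB-DMARD who adds a different one within 90 days is flagged on the plain reading of criterion 4, subject to the undefined comparator.
- *Early treatment failure defines the flag.* Continued background use and planned combination starts also set it, and claims cannot tell these from add-on for poor response.

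The effect on the composite is also smaller than on criterion 4 alone. The patient who stops on day 30 and does not restart cannot reach the adherence threshold of 0.8, and so fails whatever criterion 4 says.

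**Conclusion.** The point holds in a limited form. A variable labelled baseline is determined in follow-up. Any regimen coefficient or regimen-level predicted cost based on it is open to distortion of unknown size and direction: for persistence, roughly 5 to 17 days under the one-sided assumption in step 3, none if NB-DMARD starts are unrelated to stopping, and reversed if continuers start more often. The cohort contrast shifts materially (about 2.5 to 7 days) only under strongly unequal baseline use such as 30% versus 70%.

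The firmer consequence is for secondary outcomes. Among patients with no main NB-DMARD at index, about 25% to 30% of first-year first additions would be invisible to criterion 4 and to the addition outcome, given a constant add-on hazard and annual rates of 5% to 40%. Some of those early starts will be planned combinations, so this is the share reclassified by the rule, not a count of missed failures.

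**What to change.** - In all models and predicted costs, replace the 90-day flag with NB-DMARD use in the 6 months before index, which Section 8.3 already derives.
- For criterion 4 and the addition outcome, count as an addition any select NB-DMARD that is new relative to use at or before index. Do this at least as a sensitivity analysis, since planned starts cannot be separated from add-on in claims.
- State what a different NB-DMARD is compared with for combination starters.
- Keep the 90-day label for description only.

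Do not try to repair the flag by counting NB-DMARD fills only while index-drug supply lasts. That makes the class depend on staying on the drug (immortal time). In simulation, with 10%, 20% or 30% adding within 90 days regardless of stopping, it favours combination by about 4, 8 and 13 days where the current rule gives about 0. It would also leave a day-60 add-on during treatment uncounted.

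The cost is a covariate swap, one further outcome definition in code and a sentence of clarification; no new data are needed. The downside is that a planned combination start with no NB-DMARD at or before index is treated as a non-user, and its first fill counts as an addition in that analysis.

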NB-DMARD use	Outcome	All	 For patients who initiate combination therapy, will look for select NBDMARD (MTX, SSZ, LEF, HCQ) discontinuation or switch from start of NB-DMARD through end of 12-month post-index period. Definitions of treatment patterns are similar to 5 persistent groups above for index advanced therapy medications and using a 60 day gap. A 28-day supply will be assumed for MTX administrations. For those who initiated advanced monotherapy, addition of one for four main or other NBDMARDs will be evaluated.

Variable	Role	Data source(s)	Operational definition
Medication Effectiveness Proxy Algorithm (Curtis et al) ¹⁴	Outcome	All	Medication effectiveness at one year after the index date will be determined using the following six criteria. For each of the 6 criteria, a 0/1 flag will be created. Patients who are effectively treated for each of the 6 criteria will be considered effectively treated. Patients who fail any of the 6 criteria are therefore not effectively treated.
			1.High adherence to index agent: For all medications, a proportion of days covered (PDC) will be calculated based on total days supply over the 1 year follow-up. The PDC will be calculated by using the date of service and the day supply for each fill of the index medication. Patients with early refills will be allowed to stockpile medications up to a maximum of 14 days total for later use. Patients with PDC ≥ 0.8 will be considered highly adherent and effectively treated. The original Curtis algorithm referenced an MPR;however, more recent studies are using PDCs or similarly described measure. ¹⁵

Variable	Role	Data source(s)	Operational definition
		I	2.No increase in dose (see below)
			for index medication compared to the
			starting dose. Dose escalation will be
			identified per the criteria listed
			below.
			ADA: At least 1 claim in the follow-up period with an average weekly dose of at least 40 mg/week. ETN: At least 1 claim in the follow-up period with an average weekly dose of at least 100 mg/week.
			TOFA: At least 1 claim in the
			follow-up period with an average
			weekly dose of at least 20 mg/day
			for IR and 22 mg/day for XR.
			for the and 22 mg/day for XR.
			3.No switching from the index medication to a different advanced therapy. A switch will be defined as use of a different bDMARD or JAKi any time during the follow-up period noting the availability of newer advanced therapies after original 2011 Curtis algorithm publication.
			4.No adding of a new non-biologic DMARD to the index therapy.
			Measure has been modified to
			distinguish outcomes for advanced
			monotherapy vs. NB-DMARD
			comobination regiments, noting
			patients may not have NB-DMARD in
			6-mos pre-indes but start a
			combination regimen. For those
			starting a monotherapy index
			medication regimen, the initiation of a
			select NB-DMARD will be identified
			in the follow up period as addition of
			NB-DMARD. For those starting a
			combination index medication
			regimen, presence of a different NB-
			DMARD in follow-up will be flagged
			as failing the algorithm.

Variable	Role	Data source(s)	Operational definition
			5. Oral glucocorticoids. Only National Drug Code (NDC) codes for oral glucocorticoids will be included.
			5a. For patients with no claims for oral glucocorticoid prescriptions in the six months prior to the index date: cannot receive more than 30 days of oral glucocorticoids between (index date + 89) to (index date + 359). 30 days of oral glucocorticoids will be determined by summing up the day supply of all glucocorticoids claims with a fill date between (index date + 89) to (index date + 359).
			5b. For patients with claims for oral glucocorticoids during the six months prior to the index date: No increase in oral glucocorticoid dose ≥20% during months 6- 12 after index compared to the 6 months before the index date. Increase in oral glucocorticoids will be determined from the prednisone equivalent dose for all glucocorticoid claims filled during the respective time periods.
			6. At most one parenteral or intra- articular glucocorticoid joint injection on unique days after the patient had been on biologic treatment for more than three months between (index date + 89) to (index date + 359). CPT codes 20600, 20605, 20610.
Change in Resource Use RA-related healthcare	and Costs (Tables 5 an Outcome	all	The number of patients with and number of encounters
resource use		- 141	(including zeros) for each RA- related medical and pharmacy resource use will be evaluated in the 12-month pre- and post-index periods. See Section 8.3.1 for details on calculating cost and healthcare utilization.
All-cause healthcare resource use	Outcome	All	The number of patients with and number of claims (including zeros) for each all-cause medical and pharmacy resource use will be evaluated in the 12-month pre- and post-index periods. See Section 8.3.1 for details on calculating cost and healthcare utilization.

Variable	Role	Data source(s)	Operational definition
Healthcare Costs	Outcome	All	RA-related and all-cause resource use attributable health care costs will be computed as the combined health plan/other payer (ex, Coordination of Benefits for Medicare Supplemental in Truven) and patient paid amounts.
			See Section 8.3.1 for details on calculating cost and healthcare utilization.

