8.2.1. Inclusion Criteria

Patients must meet all of the following inclusion criteria to be eligible for inclusion in the study:

- 1. The **first pharmacy claim for TOFA and then ETN or ADA** between Jan 2014 and Sep 2016 represents the index claim *(See Appendix 1 for codes)*. Selection of comparator groups will be hierchical per the following:
 - a. First, select patients receiving ≥1 tofacitinib (TOFA) pharmacy claim (Jan 2014–Sep 2016) who did not have a TOFA claim anytime prior to index.
 - b. Amongst remaining patients, select those receiving ≥1 ETN or ADA pharmacy claim, assign per whichever occurs first, over same time period (Jan 2014-Sep 2016) who did not have a respective pharmacy or administration claim for index medication anytime prior to index.
- 2. Patients do have >1 advanced therapy filled on index date.

- 3. Physician diagnosis of RA (in any position) during the 1-year pre-index period, or on the index date:
 - ICD-9 = 714.0x-714.4x, 714.81;
 - ICD-10 = M05.x, M06.0–M06.3, M06.8–M06.9.
- 4. Patients don't have claims for other conditions for which TOFA and/or advanced therapies are used, during the anytime pre-index period or on the index date.

Disease	ICD-9 diagnosis code	ICD-10 diagnosis code
Ankylosing Spondylitis	720.0x	M45.0 - M45.9
Crohn's Disease	555.xx	K50.*
Psoriasis	696.1x	L40.0*-L40.4*, L40.8*-L40.9*
Psoriatic Arthritis	696.0x	L40.5*
Ulcerative Colitis	556.xx	K51.*

Table 1. Exclusionary Diagnoses

- 5. Commercially insured or Medicare beneficiaries at index.
- 6. Continuous enrollment during 1 (360 days)-year pre- (pre-index period) and 1-year post- index.
- 7. Age 18+ years at index.
- 8. Study cohorts.
 - a. TOFA Advanced Therapy Naïve OOP Cost Cohort.
 - Identify those with no advanced therapy (bDMARDs/JAK inhibitors) anytime before index TOFA prescription.
 - b. ETN or ADA to TOFA OOP Cost and TNFi Cycling Cohort.
 - Identify those that had ADA or ETN, but not both, and no other advanced therapy anytime pre-index TOFA (*See Appendix 1*).
 - c. ADA to ETN TNFi Cycling Cohort.

- In those newly starting ETN, patient must have a claim for ADA and no other advanced therapy (*See Appendix 1*), including index ETN (pharmacy/admin claims), anytime pre- index ETN.
- d. ETN to ADA TNFi Cycling Cohort.
 - In those newly starting ADA, patient must have a claim for ETN and no other advanced therapy (*See Appendix 1*), including index ADA (pharmacy/admin claims), anytime pre- index ADA.

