8.7.2. Secondary Objectives

8.7.2.1. Explore the Differences in Demographic and Clinical Characteristics Between TOFA Index Prescription OOP Costs and TNFi Cycling with ETN and ADA vs. TOFA Switching Cohorts

For this objective descriptive analysis will be conducted. The goal of this objective will be to describe the respective cohorts and explore the presence of demographic and clinical characteristics differences between the cohorts that will inform multivariable analyses. Known demographic characteristics (eg, age, gender, geographic location) will be summarized. In addition, other patient characteristics (eg, pre-index RA medication use and medical history, comoribidity status, cumulative/index OOP costs) will be evaluated. Index medication prescriber, regimen, and OOP costs will also be described.

8.7.2.2. Compare Treatment Patterns Including Dosing, Adherence, Persistence Treatment Patterns Between TOFA Index Prescription OOP Costs and TNFi Cycling with ETN and ADA vs. TOFA Switching Cohorts

For this objective, treatment patterns will be summarized across the cohorts of interest. Specific treatment patterns include changes in use of concomitant NB-DMARDs, number and proportion of patients in the five treatment persistent groups (persistent, switch immediately, discontinue and switch, discontinue and restart, discontinue and no switch or restart), switch anytime, or effectively treated (meeting each of 6 Curtis algorithm criteria) as well as times to immediate and anytime switch and discontinuation. Times to discontinuation, switching or either will be assessed with Kaplan-Meier curves and Cox proportional hazards models. 8723 Compare All-Cause and RA-Related Health Care Utilization Between TOFA

8.7.2.3. Compare All-Cause and RA-Related Health Care Utilization Between TOFA Index Prescription OOP Costs and TNFi Cycling with ETN and ADA vs. TOFA Switching Cohorts

For this objective descriptive analysis will be conducted. All-cause and RA-related pharmacy and medical resource utilization measures (flags and 12-month counts) will be presented per patient during the 12-month baseline and follow-up periods. In addition, changes from baseline to follow-up will be evaluated.

8.7.2.4. Compare All-Cause and RA-Related Healthcare Costs Between TOFA Index Prescription OOP Costs and TNFi Cycling with ETN and ADA vs. TOFA Switching Cohorts

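### Concomitant NB-DMARD discontinuation is counted over about 270 to 360 days depending on when the first post-index fill falls, so crude group proportions depend partly on fill timing

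*Combined protocol and SAP*

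**What the plan says.** Four parts of the protocol bear on this point.

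- **Who is a combination starter (8.3, index combination vs. monotherapy regimen status).** Patients using methotrexate, sulfasalazine, hydroxychloroquine or leflunomide "within 90 days on or after the index date will be considered as being treated with combination therapy regimen". The same row adds that combination patients will be stratified by NB-DMARD use in the six months before index.
- **What is followed (8.3, NB-DMARD use).** For these patients the plan looks for NB-DMARD "discontinuation or switch from start of NB-DMARD through end of 12-month post-index period". The classification is borrowed from the index drug: "Definitions of treatment patterns are similar to 5 persistent groups above for index advanced therapy medications and using a 60 day gap".
- **When follow-up ends (8.3, opening paragraph).** "The primary post-index period is 12 months including the index date". The effectiveness algorithm in the same section uses the limits "index date + 89) to (index date + 359", which puts the last day at day 360. Section 8.2.1 gives 360 days explicitly only for the pre-index year: "Continuous enrollment during 1 (360 days)-year pre- (pre-index period) and 1-year post- index".
- **How it is reported (8.7.2.2).** Treatment patterns are summarised across cohorts: "Specific treatment patterns include changes in use of concomitant NB-DMARDs, number and proportion of patients in the five treatment persistent groups". A later sentence in that section plans Kaplan-Meier curves and Cox models for times to discontinuation, switching or either, without naming NB-DMARDs. The days-to-discontinue variable in 8.3 is defined for the index medication and counted from the index date.

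**The concern.** For the index drug, every patient is classified over the same 12 months from the same time zero. The NB-DMARD outcome takes over the five groups and the 60-day gap but not the common window. A patient whose first fill is on the index date can be seen to stop at any time in the year. A patient whose first fill comes about 90 days later has roughly three quarters of that time. With identical behaviour, the second patient is less likely to be recorded as having discontinued or switched.

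Fill timing can vary for reasons unrelated to stopping. A continuing user who collected a 90-day supply just before index would next fill near day 90, whereas a newly added drug could be filled on the index date. If one cohort had more late first fills, its crude discontinuation proportion would be too low, and a small false difference could appear or a small real one be masked.

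**Working it through.** The plan states no discontinuation rate, window length or sample size for this outcome, so there is no figure of its own to reproduce. Window lengths below come from the protocol; all rates and mean start days are assumptions.

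**1. Time at risk.** Window = year length − start offset.

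| Year length | Last start offset | Shortest window | Longest window | Ratio |
|---|---|---|---|---|
| 360 | 89 | 271 | 360 | 0.753 |
| 360 | 90 | 270 | 360 | 0.750 |
| 365 | 89 | 276 | 365 | 0.756 |
| 365 | 90 | 275 | 365 | 0.753 |

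If the 60-day gap must finish inside the window, the time in which a gap can begin is 60 days shorter. For a 360-day year and offset 90 that is 210 to 300 days, a ratio of 0.70.

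**2. Patient-level extreme.** Assume a constant hazard, with proportion p discontinuing over the full window. The proportion seen by the latest starter is 1 − (1 − p)^(270/360), or 1 − (1 − p)^(210/300) if the gap must be completed.

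| p (full window) | 270-day window | Shortfall (points) | Gap completed | Shortfall (points) |
|---|---|---|---|---|
| 30% | 23.5% | 6.5 | 22.1% | 7.9 |
| 40% | 31.8% | 8.2 | 30.1% | 9.9 |
| 50% | 40.5% | 9.5 | 38.4% | 11.6 |

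Example: 1 − 0.60^0.75 = 31.8%, and 40.0 − 31.8 = 8.2 points. These rows compare a patient starting at index with one starting 90 days later; they are not expected cohort differences.

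**3. Cohort-level artefact.** Take two cohorts with the same hazard and different mean start offsets m, with the gap required to finish in the window. The proportion seen is approximately 1 − (1 − p)^((300 − m)/300).

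| Assumed mean starts | p = 30% | p = 40% | p = 50% |
|---|---|---|---|
| day 20 vs 25 | 0.43 | 0.53 | 0.61 |
| day 15 vs 30 | 1.28 | 1.59 | 1.83 |
| day 15 vs 45 | 2.59 | 3.23 | 3.72 |

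Example: p = 40%, day 15 gives 1 − 0.60^(285/300) = 38.45%; day 45 gives 1 − 0.60^(255/300) = 35.22%; the difference is 3.23 points. Without the completed-gap requirement (300 replaced by 360) it is 38.71% − 36.04% = 2.67 points.

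**4. Sensitivity to the hazard shape.** If stopping is front-loaded (assumed Weibull shape 0.5, 40% by day 360), the proportion seen by time t is 1 − 0.60^√(t/360). At 270 days the shortfall is about 4.2 points, and at 330 days about 1.3. Under a constant hazard the corresponding shortfalls are 8.2 and 2.6 points (40.0% vs 37.4% for the latter).

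**5. With equal windows.** If every patient is observed for the same number of days from NB-DMARD start, cohorts with the same hazard differ by 0 points on account of window length. A fixed 270 days is available to everyone: a start at index + 90 followed through index + 359 gives 359 − 90 + 1 = 270 days.

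**The case against.** The strongest reply is that unequal windows alone do not bias a cohort comparison. All cohorts share the same 90-day rule and the same end of follow-up, and nothing in the protocol says that tofacitinib, etanercept or adalimumab starters, or high- and low-OOP patients, fill NB-DMARDs at different times. This stands. A reader might infer that the plan builds in a false cohort difference of 6.5 to 9.5 points. The documents do not support that: those figures need one group starting entirely at index and the other entirely 90 days later, under an assumed constant hazard.

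Three further replies carry some weight.

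- **Stratification.** Splitting combination patients by six-month pre-index NB-DMARD use would separate new from continuing users, the most obvious source of timing differences. However, it sits in a baseline-characteristic row, is not carried to this outcome, and does not equalise windows within a stratum.
- **Planned time-to-event methods.** The Kaplan-Meier and Cox sentence in 8.7.2.2 follows the one listing NB-DMARD changes and could be read to cover them. It does not say so, and the only days-to-discontinue definition has the wrong drug and time zero for this purpose.
- **Indirect wording.** Comparing NB-DMARD proportions in five groups is inferred from the cross-reference in 8.3 together with 8.7.2.2. NB-DMARD discontinuation is not among the outcomes named for modelling in 8.7.4 or 8.7.6. That limits the importance of the point without removing it.

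Finally, start of NB-DMARD is undefined for patients already taking the drug. If it meant index or earlier for them, their window would not be shortened. Reading it as the first fill on or after index fits the 90-day rule, but the text should say so. Describing status at the end of the index-anchored year is also legitimate, provided it is not read as risk over equal time.

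**Conclusion.** The point holds in a limited form. As written, the rule gives combination starters unequal time at risk, from about 270 to 360 days, and no section equalises or censors it for NB-DMARDs. Crude proportions in the five groups are therefore affected by first-fill timing within every cohort.

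Between cohorts, distortion arises only if that timing differs. It is then roughly 0.4 to 4 points for assumed differences of 5 to 30 days in mean start and 30% to 50% discontinuing, under a constant hazard. Front-loaded stopping would make it smaller. The documents supply neither rates nor start dates, so whether any distortion occurs, and in which direction, cannot be settled from them. The 360-day year is itself inferred for the post-index period; a 365-day year leaves the conclusion unchanged.

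This is a minor matter for a secondary, descriptive outcome. A reader might suspect that the primary persistence result is affected as well. It is not, because index-drug persistence is counted from the index date over a common 12 months.

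**What to change.** 1. In 8.3, NB-DMARD use, define start as the first NB-DMARD fill on or after the index date, for new and continuing users alike.
2. In 8.7.2.2, state that the Kaplan-Meier and Cox analysis also covers NB-DMARD discontinuation or switch, with time zero at that fill and censoring at the end of the 12-month post-index period.
3. If proportions in the five groups are also compared between cohorts, report them over a fixed 270 days from that fill.

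The cost is a definition line, a sentence in the analysis section and a date shift in the program, using data already held. The time-to-event analysis discards no follow-up. The fixed-window summary leaves up to about 90 days of late follow-up unused and ends on a different post-index day for each patient, a small price for equal time at risk.
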